### Use of the device

When using the device, the dental assistant stands behind the chair and holds the “wrists” and “hands” of the device in each hand. The dental assistant then moves the jaw braces into place relative to the patient's jaw with no air pressure in the system. When there is no air pressure present, the “shoulder”, arm”, “wrist”, and

“hand” move freely without resistance. When the brace is positioned correctly on the patient’s jaw, the dental assistant presses on the foot switch to pressurize the system with air. This pneumatically locks all parts into the desired position. When removing the device, the dental assistant stands behind the chair and holds the brace with their hand and pushes on the foot switch to eliminate the pressure in the system. Then the assembly can be freely moved and placed behind the dental chair. There is also an e-stop button on the control box that can be used to evacuate the air in the system whereby the assembly is again de-activated and can be moved.

### ***6.1.1 Acquisition***

The device will be provided to the participating OMS by the sponsor. The study engineer and study coordinator will bring the device to the OMS’s office, set it up and provide instruction on use of the device. The office will also receive a FDA Label and Instructions for the device.

### ***6.1.2 Formulation, Packaging, and Labeling***

Label and Instructions for Use of the Jaw Support Device

**INTENDED FOR PREMARKET PRACTITIONER PREFERENCE TESTING ONLY**

**MANUFACTURED and Packed by:**

Lab 651  
[name]  
[name]  
[name]

**DISTRIBUTED BY:**

The Restful Jaw Company, LLC  
[name]  
[name]

For product or technical information, contact [name].

**CONTENTS:** 1 Jaw Support Device

**CAUTION: INVESTIGATIONAL DEVICE. LIMITED BY US FEDERAL LAW TO  
INVESTIGATIONAL USE.**

## **INTENDED PURPOSE:**

This device is for use during the premarket clinical investigation to support the mandible of a patient during oral and maxillofacial surgical procedures including surgical removal of third molars with moderate to deep sedation or general anesthesia.

## **USE:**

This device is fully assembled when shipped. To use, the device MUST be securely attached to the dental chair head rest post. See the chair manufacturer's instructions for removing and reinserting the chair head rest post.

[figure not shown]
The device requires air pressure to operate. Air hoses are provided with the device to connect it to the air supply in the operatory. If there is no air supply available, then a free-standing air compressor or pressurized tank is used. The air hoses are attached to the back of the chair where quick disconnect fittings are provided to hold them in place.

## **ATTACHING THE DEVICE TO THE CHAIR**

[figure not shown]
1. Remove the head rest post from the chair.
2. Hold the device with the three black knobs facing you. Turn the center black knob to loosen the head rest mounting plate. See red circle on Figure 1a.
3. Slide the device onto the head rest post so that the knobs are facing away from the front of the head rest towards the back of the chair as shown in Figure 1a.
4. Adjust the position of the device on the head rest post so the device shoulders (shown in Figure 1a in a yellow circle) can rotate freely below the arm rest pads as shown in the blue circles in Figure 1a. If needed, remove the arm rest pads from the head rest.
5. Hand-tighten the center black knob securely to lock the position of the device on the head rest post.
6. Slide the head rest post back onto the chair. Make any adjustments so the device is positioned evenly on the chair head rest post. Note: The device can contact the top of the chair.
7. Once in position, follow chair manufacturer's instructions to lock the head rest post onto the chair, commonly a large knob on the back of the chair. Once the head rest is locked, check that you can still freely rotate the arms without obstruction from the chair or arm rest pads.
8. Ensure a tight fit of the device on the post AND the post in the chair before using the device on any patient. Tighten as needed. Before every procedure always tighten the middle black knob securely. See red circle on Figure 1a.

9. See Figure 1b for a view of the device from the front when the device is in place on the chair and the patient.

**FIGURE 1a: Jaw Support Device  
(Back View)**

[figure not shown]
**FIGURE 1b: Jaw Support Device  
(Front View)**

[figure not shown]
## CONNECTING THE DEVICE TO AIR

1. Turn on the in-office air compressor, or if using a free-standing air compressor turn it on and charge to maximum tank pressure. A pressurized free-standing tank can also be used. Connect the air compressor or tank hose to the 'supply' port on the device control box shown in the orange circle on Figure 2. Note: The control box is strapped to the back of the chair.
2. Attach air hoses to all four air intake connectors on the shoulder and the end of each arm. See purple circles in Figure 3.
3. Connect air hoses to control box 'output' ports shown in purple-dashed circles in Figure 2.
4. Connect the input and output of hoses of the foot switch (Figure 4) to their respective ports on the control box shown in the blue square Figure 2. The foot switch will be used to lock and unlock the arms (Figure 4).

**FIGURE 2 Control Box**

**FIGURE 3 Device Air Ports**

**FIGURE 4 Foot Switch**

[figure not shown]

#### **POSITIONING THE DEVICE ON THE PATIENT ON BOTH SIDES OF THE MANDIBLE**

1. Seat the patient in the chair.
2. Adjust the head rest position as needed. Ensure the arm rests do not inhibit motion of the shoulder joints (see blue circles in Figure 1a).

3. Loosen the left and right knobs shown in green circles in Figure 1a.
4. Rotate the left shoulder part so the arm will extend slightly above the patient's left shoulder. Tighten left knob.
5. Repeat #3 and 4 with right shoulder.
6. Stand behind the patient and position **both** padded jaw braces at the same time under the mandible on both sides. Figure 5 shows the approximate position of the brace on the patient.
7. Press the foot switch to secure the device's position on the patient.

[figure not shown]
**FIGURE 5 Bilateral Mandible Support**

### **REMOVING THE DEVICE**

1. To remove the device, press the foot switch to release pressure in the arms. This will make the arms relax.
2. Slide the arms back to their original position near head rest.
3. Loosen the left and right knobs shown in Figure 1a, and rotate the arms back to the stored position behind the chair. Figure 6 shows the right arm in stored position.

**FIGURE 6: Device in Stored Position**

**STORAGE**

1. The device can be stored on the head rest post with the arms slid back and folded in a 90° angle as shown in Figure 6.
2. It can also be completely removed from the chair and stored in a dry place at room temperature for future use.
3. Review the chair manufacturer's instructions for removing and re-inserting the head rest on the chair post.

**MAINTAINANCE AND INFECTION CONTROL**

Disposable pads are placed on the jaw brace. If bodily fluids are present on the device, thoroughly clean all surfaces of blood and other bodily fluids using a standard EPA-registered low or intermediate level disinfectant clinic wipes, or sprays, on all surfaces in contact with the patient, clinician or bodily fluids. The padding on the jaw braces should be discarded and replaced after each use.

**PRECAUTIONARY STATEMENTS**

If excessive force is placed on the device by the surgeon, then the device could slide to a slightly different position. However, as soon as this force is stopped, then the device will stop moving. If the device malfunctions and loses pressure during the procedure, the passively controlled arms will fall away from the patient's jaw; and the clinician or dental assistant need to be immediately available to provide support for the patient's jaw.

A red emergency air release valve *is located on the back side of the control box* and should be pushed in the event of an emergency and/or if the foot switch is malfunctioning to evacuate all air from the system.

Do not use on any patient where the device cannot be positioned correctly or appropriately adjusted on them for stability and support of the mandible.

## **PROCEDURES TO FOLLOW IN THE EVENT OF PATIENT EMERGENCY**

Remove device from patient contact:

1. If this is an emergency, support the patient's jaw and then press the foot switch.  
This will release air from the arms which will lose pressure and become relaxed.
2. Slide the arms back to their original position near head rest.
3. Loosen the right and left knobs turning the green-circled knobs as shown in Figure 1a.
4. Rotate the arms back behind the chair as shown in the stored position in Figure 6.
5. Follow clinic's protocol for emergencies.

### **6.2 Accountability Procedures for the Study Product**

The device will be set up for the OMS and will be removed by the study engineer and/or the study coordinator.

## 7 STUDY SCHEDULE

### 7.1 Screening

Patients who are planning to undergo mandibular 3rd molar surgical removal with moderate/deep sedation or general anesthesia at the office of a participating OMS will be screened for possible study participation; this may occur in the OMS office prior to or on the day of the surgery, or screening may occur *over the phone*. Office staff will review inclusion/exclusion criteria with the patient via the *Screening Questionnaire* to determine if the patient meets eligibility criteria for the trial. A laminated version of eligibility criteria (see Section 5) as well as a picture of the device will be available for use by the OMS, dental assistants or office staff when discussing the study with the patient.

The procedures listed below are consistent with those included in the Schedule of Events (Appendix A).

### 7.2 Enrollment/Baseline

If eligible and interested in study participation, the patient will undergo consent procedures via tablet technology. A designated office staff member, most likely the OMS, will execute the consent process according to IRB requirements.

If an enrolled patient declines to provide any of the essential baseline data on the *Patient Contact Information*, *Patient Demographics*, and/or the *Baseline Patient Questionnaire*, this decision will be considered a voluntary withdrawal from the study (see Section 5.5.1).

#### Enrollment/Baseline Visit (Visit 1, Day 0)

- Verify, obtain and document consent from potential patient via electronic data capture consent form based on IRB requirements.
- Verify and document Health Insurance Portability and Accountability Act (HIPAA) authorization for use of the patient's Personal Health Information (PHI) in Research, based on IRB requirements.
- Patient completes patient contact information, patient demographics information, and *Baseline Patient Questionnaire*.
- Record results of TMD examination from OMS on *Doctor Surgery Questionnaire*.

- After a patient eligibility is confirmed and they have provided consent, the patient's random assignment to EC or UC is then automatically available to the OMS and their dental assistant on the tablet. The patient is then informed of their group assignment.
- OMS completes usual care extraction of 3rd molars with moderate/deep sedation or general anesthesia and bite block. If patient is randomized into the UC group, the procedure will be completed with a bite block and a DA holding the jaw. If patient is randomized into the EC group, the procedure will be completed with a bite block and the RJ2 device.
- OMS completes *Doctor Surgery Questionnaire*.

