## 2.3 Potential Risks and Benefits

### 2.3.1 Potential Risks

There are potential risks of using the RJ2 device. If excessive force is placed on the device by the OMS, then the device could slide to a slightly different position. However, as soon as this force is stopped, then the device will stop moving. There is potential that the device could malfunction and lose pressure during the procedure. If this occurs, the passively controlled arms will fall away from the patient's jaw which could also compromise the support of the patient's jaw. To mitigate these risks, the dental assistant will be present behind the dental chair to support the jaw. Patients have similar

risk of jaw injury when their jaw is supported only by the dental assistant's hands since their hands can slip in position if excessive force is placed on the jaw, and their supporting arms and hands can become fatigued during procedures compromising their ability to support the jaw. In addition, patients could report that the padded jaw brace when placed under their jaw feels uncomfortable. If this occurs, then the dental assistant can reposition the brace to a position that is comfortable. There are no other anticipated safety risks to participating in this study beyond those risks inherent in 3rd molar extractions with moderate/deep sedation or general anesthesia. Patients do not receive 3rd molar extractions as a study procedure. Consequently, risks of 3rd molar extraction with moderate/deep sedation or general anesthesia will be discussed with the patient as part of normal clinical care and are not considered to be study-associated. Finally, if any adverse event (AE) occurs, then it will be documented and assessed by the study team.

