#### 3.2 Study Outcome Measures

##### 3.2.1 Primary

The primary outcome is the incidence of TMD pain within a 6-month follow-up period (binary dependent variable). TMD pain is deemed to have occurred if the patient's self report in the *Patient 1-, 3- and 6-month Follow-up Questionnaires* endorses either or both of the following questions: Pain in jaw with wide opening, or pain in temples, jaw joints or jaw muscles. The primary analysis will include all available follow-up measures (1, 3, and 6 months) for each patient to estimate the incidence of TMD pain.

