Patient-reported data will be collected via tablets, smart-phones, or computers at baseline during in-office visit(s) with the surgeons. To assist with in-office data collection, participating OMS will be offered tablets. OMS, dental assistants, and patients will provide baseline and follow-up data directly into the electronic data capture (EDC) system that is maintained by the HealthPartners Data Coordinating Center (DCC); data can be entered via tablets, smart-phones, or computers. After baseline, patient-reported data will be ascertained independent of office visits, and all follow-up patient, OMS and dental assistant data collection will be managed by HP DCC. Follow-up contacts to non-responders will also be managed by the DCC.

- **Overview of Study Schedule**

- The electronic data system used to collect patient and OMS/dental assistant data will be assessed for acceptability and compatibility prior to administration of any questionnaires.
- OMS and their office staff will receive study training from the Study Coordinator (SC), after which the OMS is authorized to begin enrolling study patients.
- An in-office patient log will be kept regarding the reason patients were excluded or declined to participate.
- Once the patient is screened using the *Screening Questionnaire* that comprises the inclusion and exclusion criteria, patients who are eligible will be invited to participate in the study. Potential patients who are interested in study participation will undergo consent procedures.
- Patients will complete these baseline forms and questionnaire before surgery: *Patient Contact and Patient Demographics information*, and *Patient Baseline Questionnaire*.
- Randomization procedures will occur, and patients will receive their randomized assignment.
- The OMS will complete the *Doctor Surgery Questionnaire* after completing the 3rd molar extractions.
- At 1, 3, and 6 months post-baseline, patients will complete follow-up assessments via an online questionnaire. Non-responders will be followed up with email, telephone, and/or texting. All patients will be followed up regardless of whether they report TMD pain at any follow-up.

- Midway through and at the end of the enrollment phase of the study, the OMS and dental assistants will complete a questionnaire regarding their experience with the use of the device.

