#### **5.4.2 *Masking Procedures***

In this RCT, it is not feasible to blind patients, surgeons, or dental assistants to treatment after the intervention assignments have occurred, so they will not be blinded. It is, however, feasible to mask the sequence of treatment assignments until the moment each assignment is made, and this will be done, as described in Section 5.4.1, above.

The DCC will also be un-blinded to treatment arm assignment. However, study staff and investigators will not have access to any interim outcome data. Unmasking procedures during the surgery will not be necessary as the patient, surgeon, and dental assistants will be un-blinded to the treatment group for each patient. The patient's record in the OMS office will include documentation of study participation and their group assignment (i.e., UC versus EC).

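### Patients are told their arm before surgery, without a patient-specific reason, although the primary and all between-arm secondary outcomes are their own reports

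*Combined protocol and SAP*

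**What the plan says.** Section 7.2 (Enrollment/Baseline Visit) makes the assignment available on the tablet to the surgeon and assistant once eligibility and consent are settled. It then adds: "The patient is then informed of their group assignment". The extraction is the next step: "OMS completes usual care extraction of 3 rd molars with moderate/deep sedation or general anesthesia and bite block". The Section 4 overview agrees: "Randomization procedures will occur, and patients will receive their randomized assignment". Section 5.4.1 also has the surgeon or assistant give the participant the assignment.

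Section 5.4.2 explains the open design in one statement covering three groups: "it is not feasible to blind patients, surgeons, or dental assistants to treatment after the intervention assignments have occurred". It gives no reason and does not treat patients separately. The only masking described is of the allocation sequence. The same section leaves the data coordinating center (DCC) unblinded and places the assignment in the patient's office record.

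On the outcome, Section 3.2.1 says: "TMD pain is deemed to have occurred if the patient's self report" endorses either of two pain questions at 1, 3 or 6 months. In Section 3.2.2 the outcomes compared between arms (pain screener, pain intensity, joint noise, pain characteristics, change in pain) all come from the same patient questionnaires.

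**The concern.** Surgeons and assistants plainly cannot be blinded. For patients the case is less clear. All of them have moderate or deep sedation or general anesthesia, and the arms differ in what supports the jaw during the extraction. Telling the patient is not needed to deliver either treatment.

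Knowledge of the arm can change how a patient answers questions about jaw pain over the next six months. The trial tests whether a new jaw-support device lowers reported pain, so the likeliest direction is fewer endorsements in the Experimental Care (EC) arm, more in the Usual Care (UC) arm, or both. No examiner-assessed or objective outcome is compared between arms at follow-up, and no planned analysis could separate a reporting difference from a device effect.

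**Working it through.** **Passages side by side**

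- Disclosure is a planned step before surgery (Sections 4, 5.4.1 and 7.2), not an accident of the procedure.
- Some features favour withholding it. The tablet controls when an assignment is revealed (Section 5.4.1). Follow-up does not depend on office visits (Sections 7.3 and 7.4). The instructions for use allow the device to stay on the chair: "The device can be stored on the head rest post with the arms slid back and folded".
- Section 5.2 excludes patients whom the device does not fit, and Section 5.4.1 gives the assignment only after eligibility is confirmed. Together these imply that fit is judged in every patient before assignment. The documents do not say how.
- Other features work against masking. Section 8.1 positions the device before the procedure in EC patients only. Section 2.3.1 expects that a patient may find the brace uncomfortable, and then "the dental assistant can reposition the brace to a position that is comfortable". That describes a responsive patient who can notice the device. The order of placement and sedation is not stated.

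**The plan's own figure**

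Section 12.2 gives 132 per group for 80% power, two-sided alpha 0.05, incidence 14% and relative risk 2.0. With 14% as the lower arm and 28% as the higher, the average is p̄ = 0.21 and

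n = [1.960·√(2·0.21·0.79) + 0.842·√(0.14·0.86 + 0.28·0.72)]² / 0.14² = (1.129 + 0.478)² / 0.0196 ≈ 132.

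Allowing for 10% loss, 264/0.9 = 293.3, so 294. Both figures reproduce, and nothing in this point changes them.

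**Illustration of the bias**

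Inputs: n = 132 per arm and two-sided 0.05 (Section 12.2). True incidence is equal in both arms, at 14% or 28% (the two arms of the plan's calculation) or 20% (another row of Table 1). The reporting shift is an assumption. With reported incidences p_UC and p_EC, d = p_UC − p_EC and average p̄, the chance of a significant result favouring the device is

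Φ[(d − 1.96·SE₀)/SE₁], where SE₀ = √(2p̄(1−p̄)/132) and SE₁ = √((p_UC(1−p_UC) + p_EC(1−p_EC))/132).

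Worked case, 22.5% v 17.5%: SE₀ = √(0.32/132) = 0.0492; SE₁ = √(0.31875/132) = 0.0491; (0.05 − 0.0965)/0.0491 = −0.946; Φ = 0.172.

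| Assumed reporting shift, no true effect | Reported UC v EC | False result for device |
|---|---|---|
| None | equal | 2.5% |
| EC 10% relative under-reporting, true 14% | 14.0% v 12.6% | 5.2% |
| EC 10% relative under-reporting, true 28% | 28.0% v 25.2% | 7.4% |
| EC 20% relative under-reporting, true 14% | 14.0% v 11.2% | 10.1% |
| EC 20% relative under-reporting, true 28% | 28.0% v 22.4% | 18.0% |
| 5-point gap around 20% | 22.5% v 17.5% | 17.2% |
| 5-point gap around 28% | 30.5% v 25.5% | 14.5% |

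A 10-point gap would give 52.9% around 20% and 44.0% around 28%. Nothing in the documents shows that a shift of that size is likely.

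The calculation uses one binary outcome per patient, the same simplification as Section 12.2. The planned GEE over three visits would give somewhat different figures. It would not remove the bias, because a reporting difference present at each visit goes straight into the group comparison.

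**The case against.** The open design is stated frankly, and many device trials cannot blind patients. Parts of this protocol also support the sponsor's position. EC patients may feel the brace while responsive, and moderate sedation, which is eligible, may leave some recall. Section 7.1 has a picture of the device on hand when the study is discussed with patients, so some could recognise it. The arm is in the office record, and Section 7.7 lets patients with jaw pain return to a surgeon who knows it. Follow-up is not wholly online either: Sections 4 and 5.3 offer completion by telephone, in Section 5.3 with the unblinded DCC.

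These points stand, and they rule out three stronger readings. A reader might infer that the arms differ only while the patient is unaware, so that silence alone would blind; Sections 2.3.1 and 8.1 do not support this. A reader might infer that the announcement comes just before sedation; the documents give the order of steps but not when sedation starts. A reader might infer that most of the bias could be avoided; that is plausible but not shown.

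The size of the shift is also assumed, and the direction is an inference, since the text available for review does not show what patients are led to expect of the device. None of this justifies telling every patient. Imperfect masking is a reason to measure how well it worked. Nor does it supply the missing patient-specific reason in Section 5.4.2.

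**Conclusion.** The point holds in a limited form. The protocol deliberately discloses the arm to every patient before surgery, asserts infeasibility without a patient-specific reason, and relies on patient self-report for the primary and all between-arm secondary outcomes. This adds an avoidable source of bias, probably favouring the device, of unknown size. Under the stated assumptions (no true effect, 132 per arm, one binary outcome), relative under-reporting of 10% to 20% in EC takes the false-positive chance in the device's favour from 2.5% to about 5% to 18%, and a 5-point absolute gap to about 15% to 17%.

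The trial remains a valid randomized open-label comparison, and its sample size is unaffected. It does not follow that a positive result would be an artefact, only that the plan has no means of telling how much of it is. The change is worth making because it is cheap, not because it would secure full blinding.

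**What to change.** 1. In Section 7.2, delete "The patient is then informed of their group assignment". Amend the matching wording in the Section 4 overview and in Section 5.4.1. Have the tablet show the assignment to the surgeon and assistant only; patients may use tablets for baseline data, so the display needs restricting.
2. In Section 5.4.2 and the consent form, state that staff will not disclose the arm to patients until the 6-month questionnaire is closed. If the sponsor still considers this infeasible for patients, give the reason for patients specifically.
3. State that DCC staff who take questionnaires by telephone neither see nor mention the arm.
4. Add one item at 6 months, after the outcome questions, asking which jaw support the patient believes was used. Report the answers by arm.
5. Reconcile Sections 2.3.1, 5.2, 5.4.2, 7.2 and 8.1 on how device fit is checked before assignment and on the order of device placement and sedation. That order is for the sponsor and surgeons to settle; this review does not propose one.

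The cost is protocol, consent and training wording, a tablet display setting, an access restriction at the DCC and one questionnaire item. The numbers stay at 132 per group and 294 randomized. The downside is that masking will be partial: some patients may notice or recall the brace, the office record shows the arm, and some will return to an unblinded surgeon. The added item shows how far this happened.
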